8.2.2 Regional Study Site Qualifications

In the US, only individuals that are not on the FDA debarred list will be selected for participation. In addition to the FDA debarred list, other lists will be checked for investigators that will be excluded from participation (i.e. Disqualified/Restricted/Assurances List, Notice of Initiation of Disqualification Proceedings and Opportunity to Explain, Public Health Service listing).

For countries outside the US (e.g., EU), comparable lists might be prohibited according to local law. In these countries, the above mentioned evaluation will be performed as applicable.

In order for a regional study site to become qualified to provide MRI imaging for this study, it must meet the following criteria:

- Agree to follow the study imaging protocol
- Receive training
- Perform an acceptable test scan
- Be certified to meet the specifications for the study by a representative from the central Imaging Core Laboratory prior to performing study-related imaging
- Perform study MRIs on a 1.5T or 3 Tesla MR scanner made by Siemens, General Electric, or Philips

- Have, or be approved to purchase and installed by the first time patient is enrolled, the required equipment as described below:
 - Aorta: Phased array body/cardiac coil (of 4 channels or more) or equivalent coil determined in consultation with the central Imaging Core Laboratory for imaging of the aorta (anterior and posterior elements)
 - Carotid: Bi-lateral 4- or more channel multi-channel phased array carotid coil or equivalent coil determined in consultation with the central Imaging Core Laboratory
 - Cardiac gating and pulse gating system compatible with respective vendor platform
 - Capability to transfer imaging data by Secure FTP (file transfer protocol) to a location external to site firewall or send the images to the central Imaging Core Laboratory by courier

In addition, the regional study site must perform all other activities associated with being an investigational site, including patient screening and enrolment, MRI imaging, blood draws and processing, patient follow-up, and data storage and transfer.

8.3 Variables

8.3.1 Patient Data Collection

For patients enrolled in this substudy, all of their relevant individual data collected in LOWER will be included in the study database. The relevant data points will be transferred into the study database as described in a separate data management plan (DMP). Therefore, patient demographic data, medical history, and lomitapide exposure data will not be necessary to collect again in this study. A Central Laboratory will be used for this study.

8.3.1.1 Regional Study Site Enrolment Visit

At the LOWER enrolment visit, after the patient has provided written consent to participate in LOWER, the LOWER enrolling physician (or designee) will provide an overview of this vascular imaging study to each patient. The LOWER enrolling physician will notify the SCC of interested patients. The SCC will then notify the regional study

site. The regional study site will contact the patient to assess eligibility and obtain informed consent. For patients who are not located near the regional site, verbal informed consent will be obtained first by phone with written informed consent obtained at the baseline visit, prior to any procedures being performed. Enrolled patients will have a baseline MRI scan at the regional study site prior to initiating lomitapide therapy or within three months after initiating lomitapide therapy.

The following will be collected at the enrolment visit:

- Date of written informed consent
- Confirmation of eligibility criteria
- Laboratory tests (lipoprotein, inflammatory and cardiovascular biomarkers)
 - Lipoprotein biomarkers
 - Total cholesterol (TC)
 - High density lipoprotein (HDL-C)
 - Low density lipoprotein (LDL-C)
 - Triglycerides (TG)
 - Apolipoprotein B (apo B)
 - Apolipoprotein A-I (apo AI)
 - Lipoprotein (a) (Lp(a))
 - Apolipoprotein C-III (Apo C-III)
 - LDL sub-fractions using nuclear magnetic resonance (NMR) technology
 - Inflammatory and cardiovascular biomarkers
 - High sensitivity C reactive protein (hs-CRP)
 - Serum amyloid A (SAA)
 - Soluble Inter-cellular Adhesion Molecule-1 (sICAM-1)
 - Interleukin 6 (IL-6)
 - Lipoprotein Associated Phospholipase 2 (LpPLA2)
 - Soluble Vascular Cell Adhesion Protein 1 (sVCAM-1)
 - Soluble E-selectin (sE-selectin)

- Fasting glucose and insulin and calculate HOMA (Homeostasis Model Assessment)
- Baseline MRI

8.3.1.2 Baseline MRI Scan

In order to be eligible for this study, a patient must have his/her baseline MRI scan within three months after initiating therapy with lomitapide. The baseline MRI should ideally be scheduled as soon as possible after enrolment and prior to initiation of lomitapide therapy.

Patients must have a baseline MRI scan that is deemed evaluable with an acceptable image quality of carotid arteries (both left and right carotid arteries) and aorta as determined by the central Imaging Core Laboratory in order to proceed to the follow up visits. All MRI scans must be immediately sent to the central Imaging Core Laboratory for qualitative image analysis. The central Imaging Core Laboratory will provide a rapid turnaround (within one week) of the image quality evaluation. The image quality evaluation will be sent to the regional study site as well as to the SCC so that, in the event that a repeat MRI is required, the site can contact the patient to return for additional scans.

Each regional study site will provide data to the central Imaging Core Laboratory following the guidelines set forth in the MRI Imaging Facility Charter ([Section 8.3.2](#)). The central Imaging Core Laboratory will notify the regional study site and the SCC that the MRI is acceptable, or if a repeat MRI is required. The SCC will request that the regional study site Investigator or his/her designee either complete the notification form if the testing was completed or contact the patient and schedule a repeat MRI. An MRI image deemed acceptable by the central Imaging Core Laboratory must be confirmed within three months of the patient starting lomitapide treatment. If delays result in the imaging being done outside of the three month window since starting lomitapide treatment, the patient will not be eligible to continue in the study.

The central Imaging Core Laboratory will transfer analysed results to SCC in a pre-specified format and time-frame as specified in the DMP.

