8.5.1 Efficacy Endpoints

The primary objective of the study is to assess the change in carotid atheroma as reflected by carotid vessel wall area on MRI scanning following two years of treatment with lomitapide. The endpoint used to address this objective will be the percent change in carotid vessel wall area from baseline to two years on lomitapide therapy, where percent change is calculated as $100 * \{WA(24) - WA(0)\} / WA(0)$. WA(x) denotes wall area at either baseline (x=0) or 24 months (x=24). The mean area obtained from the left and right carotid arteries will be used in the primary analysis; additional analyses will consist of individual results from the left and right arteries separately. Refer to Section 8.5.2 for the derivation of wall area measurements.

The secondary objectives of the study are:

- To assess the changes in atheroma burden as reflected by changes in average aortic vessel wall area, average aortic and carotid vessel lumen area, total vessel area, wall thickness, normalized wall index and standard deviation of wall thickness on MRI following two years of lomitapide treatment compared to baseline.

- To assess the changes in atheroma burden as reflected by changes in average aortic and carotid vessel wall area, lumen area, total vessel area, wall thickness, normalized wall index and standard deviation of wall thickness following one year and five years of lomitapide treatment compared to baseline.
- To assess changes in LDL-C and other lipoproteins at one, two and five years of lomitapide treatment compared to baseline and the correlation of these laboratory evaluations with the change from baseline in MRI parameters of carotid and aortic atheroma.

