8.5.3 Analysis Populations

8.5.3.1 Modified Intent-to-Treat (MITT) Population

The modified intent-to-treat (MITT) population consists of all enrolled patients with a readable baseline MRI. The terminology “readable MRI” is an image that can be read and interpreted by the central Imaging Core Laboratory for the study. The primary analysis of efficacy will use this population. Imputation methods as outlined in [Section 8.5.6](#) will be used for missing data for the 2-year MRI evaluation for the MITT patient population.

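### An unacceptable baseline aortic image ends follow-up even when both carotids are usable, although the primary endpoint is carotid only; and the readable-MRI term that defines MITT names no vessel

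*Protocol*

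**What the plan says.** Section 8.3.1.2 requires a baseline MRI with "acceptable image quality of carotid arteries (both left and right carotid arteries) and aorta". The core laboratory makes this judgement, and a patient who does not pass it has no follow-up visits. There is a safeguard: the core laboratory reports image quality within one week and, "in the event that a repeat MRI is required, the site can contact the patient to return for additional scans". The safeguard has a deadline: "An MRI image deemed acceptable by the central Imaging Core Laboratory must be confirmed within three months of the patient starting lomitapide treatment". After that the patient cannot continue.

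The primary endpoint in Section 8.5.1 does not use the aorta: "The mean area obtained from the left and right carotid arteries will be used in the primary analysis". Section 8.5.4.2 tests the same carotid quantity. The aorta enters only the secondary and exploratory endpoints (Sections 7, 8.5.4.3 and 8.5.4.4).

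The MITT population, on which the primary analysis is run, "consists of all enrolled patients with a readable baseline MRI" (Section 8.5.3.1). A readable MRI there "is an image that can be read and interpreted by the central Imaging Core Laboratory for the study". A missing two-year value in this population is imputed. Section 8.4 counts its 57 patients by the same word, and Section 8.3.1.5 allows withdrawal when the baseline scan is unreadable. None of these three sections names a vessel or refers back to 8.3.1.2.

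**The concern.** The condition for follow-up is stricter than the primary endpoint needs. If the carotids are good and the aorta is not, that patient's baseline aorta is missing whether follow-up continues or stops. Stopping adds no aortic data and gives up the carotid data.

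The second problem is that two standards sit side by side without a link: acceptable quality of three vessels in 8.3.1.2, and readable in 8.3.1.5, 8.4 and 8.5.3.1. Under 8.3.1.1 the patient is already enrolled when scanned. The status of a patient who fails on the aorta alone therefore depends on what *readable* means. At stake are patients who could answer the primary question, in a rare disease with a design that has no spare patients.

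**Working it through.** **Inputs.** From Section 8.4: effect 10%, SD 22%, two-sided alpha 0.05, power 80%, 40 evaluable, 57 with a readable baseline MRI, 15% dropout and 15% unreadable or unusable MRI. Assumed, because the protocol gives no figure: f, the share of baseline scans with acceptable carotids but an aorta that stays unacceptable after any repeat. I show 0%, 5% and 10%.

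**Step 1: the plan's own figures.** The normal approximation gives n = (22 × (1.960 + 0.842) / 10)² ≈ 38. The exact one-sample t-test (noncentral t, noncentrality 10√n / 22, n − 1 degrees of freedom) gives power 79.0% at n = 39 and 80.05% at n = 40, so 40 is reproduced. For enrolment, 40 / (1 − 0.30) = 57.1 if the two losses are added, and 40 / (0.85 × 0.85) = 55.4 if they are multiplied. The planned 57 matches the first. The sample size is not in error, but 57 × 0.70 = 39.9 leaves no slack.

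**Step 2: the patient who fails on the aorta alone.**

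| | Reading A: *readable* judged on the carotids | Reading B: *readable* means the 8.3.1.2 standard |
|---|---|---|
| Counted in the 57 (8.4) | yes | no |
| In MITT (8.5.3.1) | yes | no |
| Followed up (8.3.1.2) | no | no |
| Two-year carotid value | imputed | neither measured nor imputed |
| Where the cost falls | fewer measured outcomes | more patients scanned |

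The protocol's words fit either column.

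**Step 3: size under reading A.** Expected evaluable = 57 × (1 − f) × 0.70. Imputed share of MITT = 1 − 0.70 × (1 − f).

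| f | Barred, of 57 | Expected evaluable | Power at the rounded n | Imputed share of MITT |
|---|---|---|---|---|
| 0% | 0 | 39.9 | 80.0% (n = 40) | 30% |
| 5% | 2.9 | 37.9 | 77.9% (n = 38) | 33.5% |
| 10% | 5.7 | 35.9 | 75.5% (n = 36) | 37% |

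With multiplied losses (retention 0.85² = 0.7225) the expected numbers are 41.2, 39.1 and 37.1, with power 81.1%, 79.0% and 76.7% at n = 41, 39 and 37. These powers count measured outcomes only. Imputation is unlikely to recover much, because Section 8.5.6 relies on lipids over time and MRI results before year 2, and a barred patient has no follow-up visits in this study to supply them.

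**Step 4: size under reading B.** Patients to scan = 57 / (1 − f): 57 / 0.95 = 60, and 57 / 0.90 = 63.3, so 64. Power stays at about 80%.

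**The case against.** The strongest reply is that this is a study of carotid and aortic disease. Aortic wall area and thickness are among the key secondary endpoints in the Hochberg procedure, and requiring both vessels at baseline gives one cohort for every test. The requirement is applied on image quality before any outcome is known, so it costs efficiency and does not bias the result. That last part stands, and no bias is claimed. But one common cohort is obtained by discarding carotid data, with no aortic data in return. The aortic endpoints do not benefit either: under 8.5.4.3 they can be declared significant only after the carotid primary endpoint is.

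The repeat scan is a real safeguard, and the bar applies only when it fails or cannot be done in time. A reader might infer that any poor first aortic image excludes the patient; 8.3.1.2 does not say that. The safeguard is weakest for late entrants: 8.2.1.1 admits patients who began treatment up to three months before enrolment, while the acceptable image must be confirmed within three months of that same start.

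A reader might also infer that MITT is bound to impute these patients' outcomes, or that several of the 57 are bound to be lost. The documents do not support either as a certainty. The core laboratory makes both judgements, and if they are one judgement (reading B) these patients are outside MITT and outside the 57, nothing is imputed, and power does not fall.

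Finally, the failure rate is an assumption. Near 0% the issue has almost no numerical effect.

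**Conclusion.** The point holds as a loss of obtainable primary data and as an undefined term, not as an error in the sample size. As written, 8.3.1.2 ends follow-up for a patient with two acceptable carotids when only the aorta remains unacceptable within the window.

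At an assumed aorta-only failure rate of 5% to 10%, the cost is one of the following, not both:

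- about 38 to 36 expected evaluable patients instead of 40, with power 77.9% to 75.5% instead of 80%, if *readable* is judged on the carotids;
- 60 to 64 patients scanned to obtain 57, with power unchanged, if *readable* means the 8.3.1.2 standard.

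These figures rest on the plan's effect, SD and combined 30% loss, and on a failure rate that the protocol does not give. The size is modest, but the change is worth making because the disease is rare, the planned number has no margin, and Section 8.4 itself provides for enrolment falling well short.

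**What to change.** - In 8.3.1.2, make acceptable images of both carotids the condition for proceeding to follow-up. If only the aorta is still unacceptable after any repeat scan, keep the patient for the carotid endpoints and treat the aortic endpoints as missing.
- Use one term in 8.3.1.2, 8.3.1.5, 8.4 and 8.5.3.1, defined for the primary analysis as readable left and right carotids.
- State in 8.5.4.3 and 8.5.6 that aortic endpoints are analysed in patients with a readable baseline aorta, and that a missing baseline aorta is not imputed. Without a baseline there is no denominator for percent change, and 8.5.6 describes imputing two-year values, not baselines.

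The cost is wording in these sections and a separate, slightly smaller n for the aortic key secondary endpoints. Of 57 patients with readable carotids, 57 × 0.95 = 54.2 to 57 × 0.90 = 51.3 would have a baseline aorta at the assumed rates. Under reading A the aortic number is no lower than it would be now, because the barred patients have no usable baseline aorta in any case.

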8.2.1.1 Inclusion Criteria

- Adult patients (age ≥ 18 years) who are enrolled in LOWER
- Patients who:
 - Are initiating treatment with lomitapide at the time of enrolment in this study,
 - or
 - Have initiated treatment with lomitapide within 3 months prior to enrolment in this study
- Patients who have the ability to understand the requirements of the study, and provide written informed consent to comply with the requirements for periodic MRI assessments.

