8.3.1.5 Patient Withdrawal

Patients may withdraw from the study at any time at their own request. They may also be withdrawn at any time at the discretion of the regional study site Investigator or Sponsor if the patient's baseline MRI scan is deemed unreadable or for administrative reasons.

Patients who inform their regional study site Investigator of their intent to prematurely withdraw from the study will be asked to have a final MRI scan prior to withdrawal (unless the most recent MRI was done within three months prior to the withdrawal from the study). The regional study site Investigator will record the reason for withdrawal on the End of Study form.

Sites may not enrol additional patients to replace those who withdraw early from the study.

The study may retain and continue to use any data collected before withdrawal of consent in accordance with the original patient consent form.

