8.4 Study Size

Based on published information from a randomized, placebo-controlled study on change in carotid vessel parameters as assessed by MRI (Fayad, et.al, 2011), the standard deviation of percent change from baseline to 24 months in carotid vessel wall area was estimated to be 22%. Detection of a 10% change from baseline to 24 months in carotid vessel wall area, at a two-sided α -level of 0.05 with 80% power, requires 40 evaluable patients. In order to obtain 40 evaluable patients at the two-year primary endpoint, at least 57 patients with a baseline readable MRI will be enrolled. The 57 patients to be enrolled accounts for a dropout rate of 15% over the two-year period and a 15% unreadable/unusable MRI rate.

After 20 evaluable patients have two-year MRI evaluations, a sample size re-estimation will be performed only if the conditional power of the Z-test statistic falls within the promising zone as defined by Mehta and Pocock (Mehta et. al., 2011). Further information regarding this analysis (including maximum allowable sample size) is described in Section 8.5.5. If the conditional power does not fall within the promising zone, no sample size re-estimation will be performed and the study will continue as planned (Mehta, et.al, 2011).

Should patient enrolment be much lower than anticipated, Aegerion Pharmaceuticals will propose additional measures to increase patient enrolment including opening the sub-study to other countries or regions if necessary.

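### The three-month baseline MRI rule attaches to two different events, and the MITT definition and the target of 57 admit patients whom Section 8.3.1.2 bars from follow-up

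*Protocol*

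**What the plan says.** **The window.** Protocol Section 8.3.1.2 opens by requiring the baseline scan within three months of starting lomitapide. Further on it states: "An MRI image deemed acceptable by the central Imaging Core Laboratory must be confirmed within three months of the patient starting lomitapide treatment". The next sentence begins "If delays result in the imaging being done outside of the three month window since starting lomitapide treatment" and makes such a patient ineligible to continue. The same section allows the core laboratory up to one week for the image quality read and provides for repeat scans. Sections 3.4, 8.1 and 8.3.1.1 set the limit by when the scan takes place.

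**Entry.** Section 8.2.1.1 admits patients who "Have initiated treatment with lomitapide within 3 months prior to enrolment in this study". Enrolment and baseline imaging therefore run on the same three-month clock.

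**Who may go on.** Under Section 8.3.1.2 a patient proceeds to follow-up only if the core laboratory finds the image quality of both carotids and the aorta acceptable.

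**Who is analysed and counted.** Section 8.5.3.1: "The modified intent-to-treat (MITT) population consists of all enrolled patients with a readable baseline MRI". Readable is defined there as an image that the core laboratory can read and interpret, and missing two-year values are imputed for this population. Section 8.4: "at least 57 patients with a baseline readable MRI will be enrolled".

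**Replacement.** Section 8.3.1.5: "Sites may not enrol additional patients to replace those who withdraw early from the study". It lists an unreadable baseline scan and administrative reasons as grounds on which the investigator or sponsor may withdraw a patient. A missed window is not listed.

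**The concern.** There are two problems.

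First, the limit applies both to doing the scan and to confirming its acceptance. These events can be a week apart. Sites and the coordinating centre could treat the same late-window scan differently.

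Second, eligibility to continue depends on a scan that is acceptable and in time, while MITT and the enrolment target depend on a scan that is merely readable. The scan can follow enrolment, so an enrolled patient can be stopped by the first rule and kept by the second. The primary analysis would then include someone whom the protocol barred from follow-up, with an outcome that was never going to be measured. The same patient would fill one of the 57 places meant to yield 40 evaluable patients.

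**Working it through.** **The plan's own figures.** The inputs are from Sections 8.4 and 8.5.4.2: a one-sample t-test, difference 10%, SD 22%, "at a two-sided α -level of 0.05 with 80% power, requires 40 evaluable patients".
- Normal approximation: (22 × (1.960 + 0.842) / 10)² = 37.99, so 38.
- With the noncentral t distribution: n = 40, power 80.0%. The stated 40 reproduces.
- Enrolment, with the two 15% losses added: 40 / (1 − 0.30) = 57.1, stated as 57. Multiplied, 40 / (0.85 × 0.85) = 55.4, so 56. The stated 57 is sound on either basis.
- Expected evaluable from 57: 57 × 0.70 = 39.9, or 57 × 0.7225 = 41.2. The margin over 40 is nil or about one patient. The two allowances are for dropout and for unreadable or unusable MRI. Neither is described as covering patients stopped by the window rule.

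**The two deadlines.** Take three months as about 91 days. A scan on day 88 that is accepted on day 95 is in time by the scan date and late by the confirmation sentence. With a one-week read, the disputed zone is the last 7 days of the window: 7 / 91 = 8% of the days. This is a share of days, not of patients. Late confirmation alone has no stated consequence.

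**How the rules treat each patient.**

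| Enrolled patient | May proceed (8.3.1.2) | Meets MITT wording (8.5.3.1) | Counts toward 57 (8.4) | Replacement (8.3.1.5) |
|---|---|---|---|---|
| Readable and acceptable, scanned day 88, accepted day 95 | Yes by scan date; misses the confirmation sentence | Yes | Yes | Not stated |
| Readable, scanned after the window | No | Yes | Yes | Not stated |
| Readable and in window, but not acceptable (e.g. aorta), no acceptable repeat | No | Yes | Yes | Not stated |
| No readable baseline | No | No | No | Listed as a withdrawal reason, so the ban may be read to apply |

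The second and third rows are the defect. Section 8.3.1.2 stops these patients before any follow-up scan. Section 8.5.4.2 runs the primary test on MITT with imputed values for those missing the two-year measurement. The predictors named in Section 8.5.6 include MRI results before two years, and here nothing after baseline would exist. The third row can occur because the primary endpoint is carotid, whereas acceptability also covers the aorta.

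The fourth row is a separate, smaller conflict. Section 8.4 needs 57 patients with a readable baseline, which implies enrolling until that number exists. Section 8.3.1.5 treats an unreadable baseline as a withdrawal and bars replacement of those who withdraw early.

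**The case against.** The strongest reply is that this is loose wording with little effect. Every other statement of the limit uses the scan date, loss of eligibility attaches only to late imaging, and the confirmation sentence carries no sanction. Section 3.4 has the MRI done immediately on enrolment and Section 8.3.1.1 lists it at the enrolment visit, so most scans should be in time. The 57 is a minimum, so the sponsor may enrol more. Readable and acceptable may be meant as the same thing. All of this is fair, and it limits the point. It does not remove it: one sentence still contradicts the others, and even if the two terms are synonyms, MITT has no timing condition.

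Four stronger readings are tempting, and the protocol does not support them.
- *Every patient stopped by the rule distorts MITT and the 57.* Those with no readable baseline are outside both.
- *None of these patients can be replaced.* The ban names those who withdraw early. A missed window is not listed as a withdrawal, although administrative reasons might be stretched to cover it. The status is undefined, not barred.
- *Power falls below 80%.* If 3 of the 57 were lost, expected evaluable patients would be 54 × 0.70 = 37.8 or 54 × 0.7225 = 39.0, with power 77.7% or 79.0%. But the 3 is invented, 57 is not a cap, and these are complete-case powers while the primary analysis uses imputation.
- *Enrolment should close earlier to leave time for a repeat scan.* A patient enrolled late can still be scanned in time. An earlier cut-off would turn away late entrants whose first scan is acceptable, in a disease whose rarity the protocol stresses.

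**Conclusion.** The point holds in two parts. Section 8.3.1.2 contradicts itself on which event must fall within three months; the effect is confined to scans in about the last week that are read after the limit. And the MITT and enrolment-target definitions do not match the rule for proceeding, so a patient with a readable baseline that is out of window or not acceptable counts toward the 57 and is analysed on an imputed value with no post-baseline MRI. Section 8.3.1.5 leaves the replacement status of these patients open and sits awkwardly with Section 8.4 for unreadable baselines.

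The number of patients affected cannot be derived from the protocol and may be small. The sample size calculation itself is correct. The contradiction rests on the text alone, with no assumption needed beyond counting three months as about 91 days for the example. It should be corrected because it affects who is in the primary population and is cheap to settle beforehand.

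**What to change.** 1. In Section 8.3.1.2, reconcile the two sentences to a single deadline: the acquisition date of the scan that is later accepted must fall within three months of starting lomitapide. This matches Sections 3.4, 8.1 and 8.3.1.1 and removes nobody merely because the read took time.
2. In Sections 8.5.3.1 and 8.4, define MITT and the 57 as enrolled patients with a baseline MRI accepted by the core laboratory and acquired within the window.
3. In Section 8.3.1.5, state that patients without such a scan are screening failures, not early withdrawals under the no-replacement rule. This also settles the conflict over unreadable baselines.

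Acceptance and scan date are baseline facts, so the exclusion cannot depend on the two-year outcome. The cost is wording, and perhaps a few more patients screened to reach 57.
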